--	---

	
17. Any other unstable or clinically significant concurrent medical condition (eg, infection requiring systemic anti-infective agents) that would, in the opinion of the investigator, jeopardize the safety of a subject and/or their compliance with the protocol
 
18. Localized infection at site of injectable lesion(s) requiring anti-infective therapy within 2 weeks of the first dose of study drug.
 
NOTE: Appropriate confirmatory testing (eg, punch biopsy [PBx] with bacterial counts) must be performed to rule out the presence of infection if ambiguous, or clinical signs of infection are evident

Experimental Therapy	
INXN-1001 will be supplied by the Sponsor as a capsule for oral administration. INXN-2001 will be supplied by the Sponsor as a sterile suspension for injection. Palifosfamide will be supplied by the Sponsor as a powder in single-use glass vials.
 
Dose & Schedule (21-day cycle):
 
INXN-1001: Subjects will be directed to take the INXN-1001 oral dose in a fed state (within approximately 30 minutes following a normal meal), once daily at the same time each day (\pm1 hour), beginning on Day 1 of each cycle. Each subject will receive INXN-1001 (140 mg daily for 7 days).INXN-2001: INXN-2001 [REDACTED] IT injection administered 3 hours (\pm 30 minutes) after INXN-1001 dosing on Day 1 of each cycle. If >1 injectable lesion is present, INXN-2001 will be injected into a different lesion at each cycle, and if the number of lesions is limited, the injections will be administered in sequential rotation or at investigator's discretion. If only a single lesion is present, then repeat administrations into the same lesion are permitted, and radiologically-guided techniques may be used as available.Palifosfamide: Palifosfamide (120 mg/m²/day) will be administered by intravenous (IV) infusion over approximately 30 minutes on Days 1-3 of each cycle.
Duration of Treatment	In the absence of meeting treatment withdrawal criteria, subjects should receive 6 cycles of study treatment.
Duration of Study	The duration of this study from the time of initiating subject enrollment until the completion of survival follow-up is anticipated to be approximately 34 months.

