14. Centralized registration of eligible subjects will be completed according to a process defined by the Sponsor. During Part 1 of the study, subjects will be registered by the Medical Monitor to one of the treatment arms; during Part 2, subjects will be randomly assigned to a treatment arm.
15. Appropriate cancer staging procedures should be performed during screening. For the purpose of this clinical trial, the following imaging is expected at screening:
 - a. CT of the chest, and CT (or MRI) of the abdomen
 - b. MRI (or CT) of the brain, if brain metastasis are known or suspected
 - c. CT or MRI of other anatomical regions as clinically indicated

All imaging should be of diagnostic quality and include IV contrast. PET imaging is an acceptable alternative modality provided the CT component is of diagnostic quality as per RECIST 1.1 guidelines.

For subjects with measurable lesions, target lesions should be selected and measured as per mRECIST v1.1 guidelines. ([Appendix 4](#)) Lesions that will be/are injected with INXN-2001 and/or biopsied should not be selected as target lesions, but should be assessed qualitatively as non-target lesions.

Disease sites are to be imaged throughout the study using the same method(s) used at screening. Chest and abdomen imaging are required for all follow-up imaging time points; images of the brain and other anatomical regions should be acquired on follow-up if positive at screening and as clinically indicated.

Tumor response assessments will occur at 12 weeks and 16 weeks (C5D1 and C6D7), and the Follow-up Tumor Assessment visit (24 weeks) for all subjects, including those who may have experienced a dose delay. In the setting of this immunotherapy, a progression observed at week 12 requires confirmation at week 16. Additional tumor response assessments may occur at the discretion of the investigator.

16. A blood sample(s) for cytokine profiling, breast cancer-associated biomarker levels (eg, MUC-1), and also INXN-1001 levels. Please refer to the Laboratory Manual for details regarding sample processing and shipment.

Screening (post-registration)

Cycle 1 - Days 2, 3, 7, and 15

Cycle 3 - Days 2, 3, 7, and 15

[figure not shown]
Cycle 5 - Day 1 (to coincide with the tumor assessment)

Cycle 6 - Days 2, 3, 7, and 15

Post-treatment Safety Assessment

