3.5 Rationale for Study Design and Dose Selection

The objectives of this Phase II clinical trial are to assess the safety and tolerability, PFS rate at 16 weeks, ORR, and immunological and biological effects of IT injections of INXN-2001 + INXN-1001 as monotherapy or in combination with palifosfamide. To provide an opportunity to monitor the safety of Ad-RTS-hIL-12 monotherapy and Ad-RTS-hIL-12 + palifosfamide (combination therapy) in subjects with breast cancer, a safety run-in will occur, with evaluation following one cycle of study drug.

The study will commence with Ad-RTS-hIL-12 monotherapy using a 140-mg dose of INXN-1001 administered daily Days 1-7 in 6 subjects (21-day cycle). Following a safety assessment, combination therapy of Ad-RTS-hIL-12 + palifosfamide (120 mg/m², Days 1, 2, 3 of a 21-day cycle, n=3) will commence. Safety in Part 1 of the study will determine commencement of randomization for Part 2.

During the conduct of this study, in addition to monitoring of safety and therapeutic efficacy, peripheral blood samples will be studied for indications of immunological and biological effects including analyses of breast cancer-associated cytokines/biomarkers. The combined clinical and laboratory data will be studied to assess for activity, and will be used in decision making for expansion of treatment arms.

The population for this study was selected as those subjects with recurrent or metastatic breast cancer (which is rarely curable with standard therapy) and accessible lesions, who are therefore considered to be appropriate candidates for clinical trials exploring new forms of treatment. Because breast cancers may be responsive to immunotherapeutic approaches (see [Section 4.1 Disease Background](#)), this subject population may potentially benefit from investigational therapy with Ad-RTS-hIL-12 alone or in combination with palifosfamide.

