6.2.3 Treatment Regimen

A combination of up to 3 investigational medications will be evaluated for safety, tolerability, efficacy, and biological effects in this trial. The small molecule INXN-1001 will be administered as oral capsules (once daily doses on Days 1-7) in combination with an IT injection of INXN-2001 (on Day 1 of each cycle). For each 21-day treatment cycle, INXN-2001 dosing will occur 3 hours \pm 30 minutes after the first dose of INXN-1001. INXN-2001 will be given as IT injections of approximately [REDACTED] 1 mL per treatment.

Following Cycle 1, if no accessible lesion for INXN-2001 injection is present (eg, due to complete resolution), then INXN-2001 should be injected into an alternate lesion or a draining, pathologic lymph node of a previously accessible lesion. A pathologic lymph node must be defined as a lesion per mRECIST ([Appendix 4](#)). The injections will be administered on the first day of each cycle throughout the study. Subjects must be adequately hydrated on each day of study drug administration. Subjects must be instructed to maintain good oral hydration on and between dosing days.

[REDACTED]

[REDACTED]

[figure not shown]
[REDACTED]

For treatment Arm C Combination

Therapy (Ad-RTS-hIL-12 + palifosfamide), palifosfamide will be administered following administration of INXN-1001 as a 30-minute IV infusion, and on Day 1 of each cycle the infusion should complete before injection with INXN-2001.

Palifosfamide will be administered intravenously at a dose of 120 mg/m²/day as a 30-minute infusion on Days 1, 2, and 3 of a 21-day cycle for up to 6 cycles.

The temporal sequence of the treatment regimens for study Arms A and C are shown in [Figure 4](#). For subjects enrolled in Arm C Ad-RTS-hIL-12 + Palifosfamide Combination Therapy, the sequence of regimens A + palifosfamide will be followed concurrently as shown below.

Figure 4. Study Arm Treatment Regimens**6.2.4 Preparation and Administration of Study Drug**

Please refer to the Pharmacy Manual for additional information.

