6.2.4.4 Preparation and Administration of Palifosfamide

Palifosfamide should be administered IV at a dose of 120 mg/m²/day, as an approximate 30-minute infusion on Days 1, 2, and 3 of a 28-day cycle, for up to 6 cycles. Palifosfamide is supplied in single-use glass vials each containing 350 mg of active product. Each vial is to be reconstituted with sodium chloride injection, USP, to a final concentration of 50 mg/mL and appropriate dose transferred into a 250 mL 0.9% sodium chloride IV infusion bag.

Note: Total cumulative time from reconstitution in vial through completed dose administration should not exceed 2.5 hours (150 minutes).

Information regarding the preparation of the palifosfamide dose will be provided in the Pharmacy Manual. The dose (mg) of palifosfamide should be calculated based on the subject's actual body weight as measured on Day 1 of each cycle. Body surface area (BSA) may be calculated as per the standard practice at each investigative center; however, the same formula should be used throughout the study when calculating a subject's BSA. The palifosfamide dose must be prepared as described in the Pharmacy Manual, and administered within permitted time window allowed for reconstitution in vial, dilution in the IV infusion bag, and through completion of the IV infusion.

NOTE:

- All subjects receiving palifosfamide must be adequately hydrated with at least 500 mL of fluids (oral or IV as appropriate), in addition to the infusion administered, on each day of palifosfamide dosing. Subjects should be instructed to maintain good oral hydration on and between dosing days.
- Electrolytes and hematologic toxicity need to be carefully monitored during clinical studies with palifosfamide.

Study treatment should be administered according to the planned 21-day treatment cycle, with treatment delays allowed for study-drug related toxicity as described in [Section 7.2.5](#). If the Day 1 visit for a re-treatment cycle is delayed for other reasons (eg, due to inclement weather), then the visit should be rescheduled to occur as soon as possible. If any non-prolonged delay for other reasons is to occur, the Medical Monitor should be consulted.

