9.4 Duration of the Study

The duration of this study from the time of initiating subject enrollment until the completion of survival follow-up is anticipated to be approximately 34 months, including 24 months for enrollment and the later of 1 year of further follow-up.

Each subject's participation in this study will last approximately 6.5 months, including:

- 28-day screening period.
- 6 cycles (18 weeks) of study treatment.

- Post-Treatment Safety Assessment visit performed 28 days after the last dose of study drug.
- Follow-Up Tumor Assessment visit performed 35 ± 7 days after the Post-Treatment Safety Assessment visit.

In addition, subjects who discontinue or complete study treatment without objective evidence of disease progression should continue to be followed until disease progression has been documented or an alternate anticancer therapy has been initiated, whichever occurs first. The active study period refers to the study period from informed consent through the Post-Treatment Safety Assessment visit.

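### Protocol Section 6.2.4.4 opens with a 28-day palifosfamide cycle, contradicting its own closing text and the 21-day cycle used in the rest of the protocol

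*Protocol*

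**What the plan says.** Section 6.2.4.4 of the protocol, on preparing and giving palifosfamide, sets the daily dose ("Palifosfamide should be administered IV at a dose of 120 mg/m²/day") and then the schedule: "infusion on Days 1, 2, and 3 of a 28-day cycle, for up to 6 cycles". Further down, the same section says: "Study treatment should be administered according to the planned 21-day treatment cycle". Its rule for a missed Day 2 or Day 3 dose holds the cycle to 21 ± 1 day.

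The other statements of cycle length agree with that later text:

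- Section 6.2.3 (Treatment Regimen), same dose and days: "infusion on Days 1, 2, and 3 of a 21-day cycle for up to 6 cycles".
- Synopsis, experimental therapy: "Dose & Schedule (21-day cycle").
- Section 3.5, describing the combination run-in: "Days 1, 2, 3 of a 21-day cycle, n=3".
- Table 1 and the overall design in Section 4.1.1.1 both use 21-day cycles.
- Section 9.4: "6 cycles (18 weeks) of study treatment".
- Footnote 15 to Tables 2A and 2B: "Tumor response assessments will occur at 12 weeks and 16 weeks (C5D1 and C6D7").

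The 28-day figure appears once. It is current text, not amendment history: the section that contains it also carries the 150-minute limit on reconstitution and infusion, which the Amendment 2 summary lists as added. The SAP does not mention palifosfamide and cannot settle the question.

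**The concern.** The combination arm should have one palifosfamide schedule. Here the dose and infusion days agree, but the interval between cycles does not, and the two statements stand in the same section. About 30 centers are planned, and Section 3.1 says the combination has not been studied in humans. A site working from the opening sentence would deliver palifosfamide at a lower rate than a site working from Section 6.2.3, under the same arm label.

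Two other rules depend on cycle length. The delay limits in Section 6.2.5 need a due date for the next cycle: a dose on day 29 is on time on one reading and 7 days past due on the other. The Arm C safety review in Section 4.1.3 follows completion of the first cycle, which is 21 or 28 days.

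**Working it through.** **Inputs.** Daily dose 120 mg/m² (Sections 6.2.4.4 and 6.2.3). Three infusion days per cycle, up to six cycles (same sections). Cycle length L = 21 or 28 days. Stated figures to reproduce: six cycles = 18 weeks (Section 9.4); C5D1 = week 12 and C6D7 = week 16 (footnote 15).

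**Step 1: reproduce the plan's own calendar.** Weeks for six cycles = 6L/7. C5D1 falls after 4L/7 weeks. C6D7 is study day 5L + 7, or (5L + 7)/7 weeks.

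| Quantity | Stated | L = 21 | L = 28 |
|---|---|---|---|
| Six cycles | 18 weeks | 126/7 = 18 | 168/7 = 24 |
| C5D1 | week 12 | 84/7 = 12 | 112/7 = 16 |
| C6D7 | week 16 | 112/7 = 16 | 147/7 = 21 |

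All three stated figures reproduce at 21 days and none at 28.

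**Step 2: planned palifosfamide exposure.**

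- Per cycle: 3 × 120 = 360 mg/m² for either L.
- Six cycles: 6 × 360 = 2160 mg/m² for either L.
- Per week: 360/(21/7) = 120 mg/m²; 360/(28/7) = 90 mg/m².
- Relative difference: 90/120 − 1 = −25% with 21 days as base; 120/90 − 1 = +33% with 28 days as base.

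**Step 3: two hypothetical consequences.** These assume a site adopts the 28-day sentence in full, with no delays or reductions.

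- *Exposure before week 16.* Cycles start on days 1, 22, 43, 64, 85 and 106 (L = 21) or days 1, 29, 57, 85, 113 and 141 (L = 28). By day 112 that is 6 × 360 = 2160 against 4 × 360 = 1440 mg/m², or 33% less. The figure depends on the cutoff, because the fifth 28-day cycle begins on day 113. By day 115 it is 5 × 360 = 1800 mg/m², or 17% less.
- *Drugs out of step.* If INXN-1001 and INXN-2001 ran on 21 days and palifosfamide on 28, the Day 1s would meet every 84 days (the least common multiple), so within six cycles only on days 1 and 85.

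The Simon two-stage sample size does not use cycle length and is unaffected.

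**The case against.** The strongest reply is that this is one stray number, not a rival calendar. It occurs once, the text below it in the same section directs sites to 21 days, and a site that followed it would break the section's own missed-dose rule. Section 6.2.3, not 6.2.4.4, is headed as the treatment regimen, and preparation is referred to a Pharmacy Manual that is not available here. Which text sites used is unknown. All of this stands, and it limits what can be claimed.

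A reader might infer several stronger things that the documents do not support:

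- *The efficacy scans would move.* Footnote 15 and Section 6.4.3 fix assessments at weeks 12, 16 and 24 for all subjects, including those with dose delays, and Section 8.4.1 counts the primary endpoint from first dose. A 28-day cycle would make the C5D1 and C6D7 labels wrong; it would not by itself shift the scans.
- *The combination would be given out of step.* Table 2B puts both drugs on a shared Day 1, and Section 6.2.3 requires the Day 1 infusion to finish before the INXN-2001 injection. The pattern of days 1 and 85 requires a site to ignore both.
- *A third of the exposure would be lost before the endpoint.* That depends on choosing day 112, as Step 3 shows.
- *Arm C results could not be tied to a regimen.* Section 8.6.3 tabulates exposure and Section 8.6.1 summarizes major violations by arm, so a different interval could be detected.

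What the reply does not do is remove the contradiction. No text sets up a separate palifosfamide calendar, and the conflict is not a redaction or a file-reading fault.

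**Conclusion.** The concern holds as an internal inconsistency in a dosing rule. The certain part is textual: Section 6.2.4.4 disagrees with itself and with every other statement of cycle length. The size, for a site that followed the 28-day sentence, is a planned intensity 25% lower per unit time. That figure assumes full doses without delays. Whether any subject was treated on the longer interval cannot be known from the documents. The conflict still needs correcting, because it concerns the schedule of a cytotoxic drug and can be removed at little cost.

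**What to change.** The sponsor should reconcile the 28-day sentence in Section 6.2.4.4 with the closing paragraph and missed-dose rule of that section, Sections 3.5, 4.1.1.1 and 6.2.3, the synopsis and Table 1, so that one cycle length appears throughout. This review does not say which. If the retained length does not fit the C5D1 and C6D7 labels or the 18 weeks in Section 9.4, those must be changed as well. The Pharmacy Manual should be checked against the result.

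For subjects already treated in Arm C, the actual interval between palifosfamide cycles should be taken from the dosing records, and anyone treated on the other interval listed as a deviation. The exposure tables and violation listings already planned can carry this.

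If only the one sentence changes, the cost is a one-sentence correction issued through the amendment process in Section 9.6, plus the manual check. If the other passages change instead, the edit is longer and reaches the visit schedule. Neither affects the sample size.

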6.2.5 Retreatment Criteria, Dose Delays and Modifications

Subjects may receive up to 6 cycles of study drug treatment. To receive each repeat treatment cycle, all treatment-related AEs must have resolved to Grade 1 or baseline and the following laboratory criteria must be met:

Hemoglobin \geq 9 g/L	eGFR \geq 60 mL/min/1.73 m ²
Lymphocytes $>$ 700/ mm ³	AST and ALT \leq 2.5 x ULN For subjects with documented liver metastases, ALT and AST \leq 5 \times ULN
Neutrophils \geq 1,500/ mm ³	Total bilirubin $<$ 1.5 x ULN
Platelets \geq 100,000/ mm ³	INR and PTT $<$ 1.5 x ULN

Clinical laboratory tests drawn pre-treatment for analysis on Day 1 of each cycle may be used for determining if the re-treatment criteria have been met, and must be reviewed by the investigator or designee prior to the next cycle of study drug administration. Two treatment delays for recovery to acceptable levels are allowed at weekly intervals up to a maximum of 14 days. In the event that a treatment-related dose delay is necessary for palifosfamide, then the next cycle of study treatment will be administered at 80% of the dose ([Table 3](#)). If an AE is clearly related to 1 study drug and not the other (in combination Treatment Arm C), then dose modification/delay is to occur for the relevant study drug (INXN-1001 and/or palifosfamide). A maximum of two dose reductions, of either INXN-1001 or palifosfamide, will be allowed.

Table 3. Dose Modifications for Palifosfamide-related Toxicity^a

ADVERSE EVENT	PALIFOSFAMIDE
Hematologic	
Platelet count <100 × 10 ⁹ /L	Delay dose of palifosfamide up to 14 days until platelet count ≥ 100 × 10 ⁹ /L, then reduce by 20%.
ANC < 1500/mm ³	Delay dose of palifosfamide up to 14 days until ANC returns to ≥ 1500, then maintain dose when restarted.
Neutropenic fever	Delay dose of palifosfamide up to 14 days until resolved, then reduce by 20%.
Any Grade 4 hematologic toxicity	Delay dose of palifosfamide up to 14 days until Grade ≤ 1 or baseline, then reduce by 20%.
Estimated Glomerular Filtration Rate (eGFR) (Appendix 5)	
≥25% up to <50% decrease from baseline ^b	Hold dose until repeat test is performed. Reduce dose of palifosfamide by 20% if confirmed on repeat test.
≥50% decrease from baseline ²	Hold dose until repeat test is performed. Discontinue palifosfamide if confirmed on repeat test.
Non-hematologic (other than creatinine or urinary electrolyte wasting)	
Not treatment-related Grade 3 if unresponsive to appropriate therapy.	Delay dose of palifosfamide for up to 14 days until Grade ≤ 1 or baseline, then reduce by 20%.
Not treatment-related Grade 4	Delay dose of palifosfamide up to 14 days until ≤ Grade 1 or baseline, then reduce by 20%.

^aWhen indicated, the maximum permitted delay of study drug administration due to toxicity and/or for confirmatory laboratory testing is 14 days.

^bBaseline eGFR determined based on the most recent serum creatinine measurement prior to study drug administration (ie, Cycle 1 Day 1 or Screening).

Subjects who experience a treatment-related Grade 4 AE, other than nausea and/or vomiting in the absence of optimal treatment with antiemetics, will be discontinued from study treatment. If, however, the subject has experienced a substantial benefit from treatment and the PI and Medical Monitor recommend continuation on the study, re-exposure to the experimental treatment may proceed on a case-by-case basis.

